7.3 The randomisation scheme

Randomisation of hearts will occur after consent of the recipient has been secured and after the heart has been deemed acceptable by the medical team. Permuted blocks will be used to randomise each heart to one of the two treatments while ensuring a 1:1 overall allocation ratio. The randomisation will be performed using the secure online platform SealedEnvelope (Sealed Envelope Ltd. 2022. Simple randomisation service. [Online] Available from: https://www.sealedenvelope.com/simple-randomiser/v1/ [Accessed 25 May 2023]). Once consent to participate in the study has been confirmed on the part of the recipient and the suitability of the heart for transplant has been confirmed, the PI, or delegated individual at the transplant recipient centre, will access SealedEnvelope, via a secure and traceable login and generate a random allocation, which will be sent via email to the randomiser and the trial manager. Please note that the randomisation procedure should not be conducted until the intention to proceed with cardiac donation to the named recipient has been confirmed. This should be after the retrieval operation has begun and the retrieval team have assessed the heart in situ and confirmed its suitability for transplant. It is routine for the recipient transplant coordinator to be contacted via telephone during the retrieval operation once suitability to transplant has been confirmed and therefore the randomisation should occur at this stage. This will not delay the retrieval operation. The retrieval team must include the instructions for delivery of both solutions at the WHO pre-operative briefing. It will be the randomiser's responsibility to inform the NORS team of the outcome of the randomisation in a timely manner, via telephone.

Each NORS team will maintain both treatments, and the equipment required to use either treatment, at all times and take both treatments with them to the retrieval centre. Once they have been informed of the treatment allocation, they will prepare and administer the treatment in accordance with the methods set out in this Protocol. Refer to the trial's 'Registration and Randomisation Guidelines for Sites' for more information.

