7.4 Blinding

The trial is single (participant) blind. Care providers involved in the transplant process cannot be blinded due to the different administration regimes for each treatment. Anyone who is not directly involved in the organ retrieval or transplant operations should not be informed of or seek to discover the treatment allocation. It will be the responsibility of the local PI in each centre to minimise the number of individuals who are aware of the treatment allocation.

Ideally, the outcome assessor who inputs clinical outcome data to the database should be blind to the treatment allocation. However, this is unlikely to be practically possible, due to the limited number of people involved in the transplant process. In order to assess the feasibility of keeping outcome assessors blind, each time an outcome assessor inputs data to the database they will be asked to record whether it would have been possible for them to remain blinded (i.e., did they already know the treatment allocation through previous involvement in the transplant). It is the responsibility of the local PI to ensure that appropriate individual(s) are in place to record clinical outcome data.

Local induction packs and training will stress the importance of the treatment allocation remaining unknown to anyone outside of the teams directly involved in performing the organ retrieval and transplant implantation procedures. However, it will be necessary to record the preservative solution and its method and volume of administration on the operation note. The CI acknowledges that any healthcare individual with access to the patient's operation notes and medical records may have access to this. However, doing so in order to discover the treatment allocation, except under the circumstances outlined below in Emergency Unblinding, would be in breach of the General Data Protection Regulation (GDPR) and the UK Data Protection Act (2018).

F-CUSToS Protocol

Version Number 2.0; Dated 30 January 2025

Access to medical records is monitored within all NHS organisations and should be reviewed by the PI where there is any concern of inappropriate access to identify the treatment allocation.

Donor family and transplant recipients should not be informed of their treatment allocation, except under the circumstances outlined below for Emergency Unblinding.

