the individual(s) designated by the PI should input this information into the database. This should be done within 48 hours of written evidence of informed consent being filed in the site file. When a potential participant is called to hospital to receive their transplant, their ongoing consent to take part in the study must be confirmed by a designated individual in that centre. Where consent is withdrawn at this stage this should be recorded by completing the withdrawal of consent form.

Donor baseline data: The donor baseline data outlined in section 7.6.1 will be accessed from the NHSBT transplant registry. This is to avoid duplication of data collection.

Randomisation: The randomisation procedure is outlined in section 7.3 of this Protocol. The outcome of randomisation should be recorded in the CRF, by the delegated individual(s) at the recipient centre.

Organ donation: The organ donation procedure will be carried out in accordance with the UK NORS Protocol. The only change to this Protocol will be the trial treatment, as outlined in section 8 of this Protocol. The outcome of organ donation and the treatment applied should be recorded in the CRF, by the delegated individual(s) at the recipient centre.

Transplant procedure: The transplant implantation procedure will proceed according to the method chosen by the implanting surgeon. There will be no adjustments necessary as a result of taking part in this trial. Operative data will be obtained from the NHSBT Transplant registry and will not need to be recorded in the CRF.

Initial outcome data collection: The delegated individual(s) in the recipient centre should input the CPOi, echocardiogram and PGD data to the database no later than 72 hours after the transplant procedure. This should be conducted in accordance with the blinding instructions laid out in section 7.4 of this Protocol.

CPOi is a calculated variable and will be obtained by uploading the following variables to the database:

- i. Cardiac Output (L/min) measured by Swan-Ganz, using the thermodilution method and taking the average of three measurements, performed as soon as possible, and not later than 1 hour, after admission to ICU.
- ii. Cardiac Output (L/min) measured by Swan-Ganz, using the thermodilution method and taking the average of three measurements, performed 6 hours +/- 2 hours after admission to ICU

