7.8 Long-term follow-up assessments

Trial closure data collection: After the 31st day after the final recruited participant has undergone their transplant the trial manager will telephone each of the PI to confirm the survival status of each recruited patient and, where a patient has died, the time to death will be measured from the date of their transplant and will be reported for all deaths due to all causes. The cause of death is to be recorded in all instances. The trial manager will also confirm with each PI the total length of in-hospital stay of any patient whose initial ICU or in-hospital stay was longer than 30 days. This should be completed within 4 weeks of the Trial Closure date.

There will be no additional long-term follow-up assessments related to participation in this trial. Long-term follow-up post-transplant is routine and life-long but will not be altered in any way as a result of participation in this trial.

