7.9 Qualitative assessments

As this is a feasibility trial, our primary outcome will be determined by numeric proportions and supplemented by qualitative assessments as follows:

Recipient decline to consent: Where an eligible recipient declines to consent to participate, the delegated individual(s) taking informed consent should document the reason for decline to consent, where provided (free text). The potential participant must be informed that they do not need to provide a reason.

Randomisation failure: Where an eligible recipient has provided consent to participate in this study and receives an eligible transplant that has not been randomised, the reason for failure to randomise should be recorded by the delegated individual(s) in the recipient centre.

Treatment allocation failure: Where an eligible recipient has provided consent to participate in this study and receives an eligible transplant that has been randomised but the incorrect treatment has been applied, the reason for the application of the incorrect treatment should be recorded by the delegated individual(s) in the recipient centre.

Blinding: Delegated individual(s) who record data in the CRFs will be asked whether they could have been blinded to the treatment allocation. Data from these questions will be assessed to determine the feasibility of blinding outcome assessors in the larger trial.

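### The blinding-feasibility question in section 7.4 counts only prior involvement in the transplant, so assessors unblinded through the CRF or operation note are recorded as blindable and feasibility can be overstated

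*Protocol*

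**What the plan says.** Section 7.4 makes the trial participant-blind. It would prefer the person entering outcomes to be blind too, but expects this to be impractical because few people are involved in the transplant process. To assess the matter, each assessor records at each data entry whether blinding would have been possible. A parenthesis explains what that means: "did they already know the treatment allocation through previous involvement in the transplant".

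Section 7.9 describes the same item differently: "Delegated individual(s) who record data in the CRFs will be asked whether they could have been blinded to the treatment allocation". No source of knowledge is named. The purpose is explicit: "Data from these questions will be assessed to determine the feasibility of blinding outcome assessors in the larger trial".

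Elsewhere the protocol says where the allocation is generated and written down:

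- Section 7.3: "the PI, or delegated individual at the transplant recipient centre, will access SealedEnvelope" and generates the allocation.
- Section 7.7: the randomisation result goes into the CRF, and "the treatment applied should be recorded in the CRF, by the delegated individual(s) at the recipient centre".
- Section 7.4: "it will be necessary to record the preservative solution and its method and volume of administration on the operation note". The protocol accepts that staff with access to the records may see this.

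Outcome entry uses the same role label: "The delegated individual(s) in the recipient centre should input the CPOi, echocardiogram and PGD data", and likewise for the 30-day data. For CPOi, section 7.7 describes the assessor transferring values from the healthcare record to the database.

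**The concern.** A feasibility study should say whether assessor blinding can work and, if not, what prevents it. The 7.4 wording recognises one obstacle, having taken part in the transplant. The protocol itself creates two others, the CRF entries and the operation note, and both lie close to the material an assessor handles. Someone who learns the arm that way, and answers the 7.4 question as worded, reports that blinding was possible.

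The answers are meant to guide the larger trial, whose planned primary outcome is PGD (section 2). If they look better than practice allows, that trial could rely on blinded assessment that does not hold up. Without the source of knowledge, the sponsor also cannot tell obstacles it could remove, such as form layout or choice of delegate, from those that would remain, such as the operation note or small teams.

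**Working it through.** The protocol gives no figure or threshold for blinding feasibility, so there is nothing to reproduce. The check is mainly textual.

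**Step 1: the two wordings.** Section 7.4 addresses the outcome assessor and restricts the source of knowledge to prior involvement. Section 7.9 addresses those who record data in the CRFs and sets no restriction. The same assessor, unblinded by the operation note, could properly answer yes under 7.4 (blinding possible) and no under 7.9.

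**Step 2: how each route is classified under 7.4, read literally.**

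- Took part in retrieval or implant: knowledge comes from involvement, so recorded as not blindable. Captured.
- Ran the randomisation or completed the allocation entry: unclear. The person may or may not regard this as involvement in the transplant.
- Saw the allocation in a CRF entry made by someone else: not involvement, so recorded as blindable. Missed.
- Saw the solution in the operation note while extracting data: not involvement, so recorded as blindable. Missed.

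**Step 3: is exposure by the missed routes ruled out?** Section 7.4 forbids uninvolved staff from seeking the allocation, asks the PI to limit who knows it, and says record access is monitored. These measures address deliberate look-up. They do not exclude incidental exposure during legitimate data extraction. No section requires the allocation entries and the outcome entries to be made by different people.

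**Step 4: direction and possible size.** Let *a* be the share of outcome forms completed by people involved in the transplant, and *b* the share of the remaining forms whose assessor learned the arm from the CRF or operation note. Neither is in the document; both are assumptions. If everyone follows the 7.4 definition:

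- recorded as blindable = 1 − a
- actually unaware = (1 − a)(1 − b)
- gap = (1 − a) − (1 − a)(1 − b) = (1 − a)b

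With a = 0.5, the recorded share is 50% throughout:

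- b = 0: unaware 0.5 × 1 = 50%; gap 0
- b = 0.25: unaware 0.5 × 0.75 = 37.5%; gap 12.5 points
- b = 0.5: unaware 0.5 × 0.5 = 25%; gap 25 points
- b = 1: unaware 0.5 × 0 = 0%; gap 50 points

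Across a = 0.3 to 0.7 and b = 0 to 1, the gap runs from 0 to 0.7 × 1 = 70 points. It is never negative.

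This gap compares could be blinded with was blind, which are different quantities. It is therefore an upper bound on the overstatement of feasibility. Exposure that the larger trial could design out, such as a visible form, does not make a yes answer wrong. Exposure that it would share, such as the operation note, does.

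**The case against.** The strongest reply is that the 7.4 question is hypothetical. It asks whether blinding would have been possible, not whether it happened. On that reading, limiting it to involvement isolates the structural barrier the protocol names, and an uninvolved assessor who saw a form may rightly answer yes. This stands for the trial's own forms, whose layout can change. It does not dispose of the operation note, which section 7.4 says must record the solution. Section 4 says the study replicates the larger trial except for its primary outcome, so that barrier can be expected to persist.

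Other replies also have weight. The protocol openly acknowledges the operation-note route, already expects assessor blinding to be impractical, and requires both the 72-hour and 30-day entries to follow its blinding instructions. The wider 7.9 wording, if it is the one used on the form, could pick up the other routes.

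A reader might go further and infer any of the following, none of which the document supports:

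- **That the data flow shows every assessor the allocation.** The operation note may be accessible, which is not the same as seen. A shared role label does not establish that the same person makes both entries, and section 7.7 names a separate form for initial outcome data.
- **That the feasibility answer is bound to be wrong.** It is correct if no uninvolved assessor sees the arm.
- **That the PGD comparison is thereby biased and carried into the larger trial's design.** Section 7.7 fixes by rule which ejection fraction and which haemodynamic set are uploaded. No section feeds this study's PGD rate by arm into the design; the 400 rests on 36% versus 22%.
- **That closure data are compromised because the trial manager receives the allocations.** Under section 7.8, "the trial manager will telephone each of the PI to confirm the survival status of each recruited patient", so the PIs supply the data, and these are largely objective.

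**Conclusion.** The point holds in limited form. Section 7.4 defines blindability more narrowly than section 7.9 and leaves out two routes to the allocation that the protocol itself creates. An assessor unblinded by either is counted as blindable, so the feasibility answer for the larger trial can be overstated, and on this account never understated.

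The size is unknown. It is zero if no uninvolved assessor sees the arm, and otherwise at most (1 − a)b, where both shares are assumptions. The conclusion also assumes that assessors answer by the 7.4 definition.

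Blinding feasibility is a supplementary assessment under section 7.9. The primary endpoint, the proportion of eligible hearts randomised and given the allocated solution, is unaffected. The change is worth making because it is nearly free and improves the answer to a question the study itself poses.

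**What to change.** 1. In sections 7.4 and 7.9, keep the item on whether the assessor could have been blinded, but use one wording in both places and drop the restriction to prior involvement. Add: *Do you know the allocation at this data entry? If so, from what source: part in the retrieval or implant; randomisation or treatment form; operation note or medical record; other?*
2. Report the could-be-blinded and actually-blind proportions separately, with the second broken down by source. The sponsor can then see which obstacles the larger trial could remove.
3. In sections 7.4 and 7.7, state that where another delegate is already on the log, the person who ran the randomisation or completed the randomisation or treatment form does not enter that participant's PGD, echocardiographic, CPOi or 30-day outcomes.

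The cost is one revised CRF question, a short addition to the delegation wording and one extra table. No additional staff are needed, because item 3 applies only where a second delegate already exists. The downside is slightly less flexible data entry at small centres.

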7.5 Emergency Unblinding

The Trial Manager will maintain an anonymised list of treatment allocations via SealedEnvelope.

The primary reason for emergency unblinding will be to allow an investigator/treating clinician rapid access to the treatment allocation, should it be required to treat the patient appropriately. As this trial is not fully blinded many of the investigators/treating clinicians may already be aware of the treatment allocation. However, emergency unblinding will be permitted in the following circumstances:

- i. In the event that a clinician, who was not directly involved in the organ retrieval or transplant implantation procedures (and therefore does not already know the treatment allocation), caring for the participant feels that they need to know the treatment allocation to treat the transplant recipient in an emergency.
- ii. In the event of a Suspected Unexpected Serious Adverse Reaction (SUSAR), where unblinding is required for reporting to the MHRA.

Emergency unblinding can be achieved in the following ways:

- i. Contact the PI who can assess the request and choose to reveal the treatment allocation where they feel it is clinically indicated;
- ii. Contact the Trial Manager who can access the list of treatment allocations and provide emergency unblinding;
- iii. Contact any member of the transplant team who was involved in the transplant procedure to reveal the treatment allocation, providing they inform the PI ex post facto;
- iv. Access the operative records themselves, provided they inform the PI ex post facto.

The PI must record the reasons for any unblinding and communicate these to the CI, as well as recording them in the site file and the medical notes. Any emergency unblinding will also be documented at the end of the trial in any final trial report.

The CI must notify the Sponsor in writing as soon as possible following unblinding detailing the necessity of the code break. The CI/PI will also notify the relevant authorities. The written information will be disseminated to the Data Safety Monitoring Committee for review in accordance with the DSMC Charter. This is the responsibility of the CI.

7.6 Baseline Data

7.6.1 Donor Baseline Data

Donor baseline data will be obtained from the NHSBT Transplant registry. The recipient identifier will be used to match to the donor identity in the Transplant registry. Collaboration with NHSBT in order to access this data via the transplant registry reduces the workload on the research and clinical teams and prevents unnecessary duplication of data collection.

- i. The following baseline data will be collected for all eligible donors:
- i. ABO blood group
- ii. Height
- iii. Weight
- iv. BMI
- v. Pathology leading to brainstem death
- vi. History of Hypertension
- vii. History of Pulmonary disease
- viii. History of cardiac disease
- ix. History of liver disease
- x. History of Diabetes mellitus
- xi. Insulin use
- xii. Renal function (serum creatinine)
- xiii. Liver function (serum bilirubin)
- xiv. History of infection during admission
- xv. Malignancy
- xvi. Left Ventricular Ejection Fraction
- xvii. Ischaemic time
- xviii. Current or past smoker
- xix. History of Drug abuse
- xx. Inotrope score

7.6.2 Recipient Baseline Data

Recipient Baseline Data will be obtained from the NHSBT Transplant Registry. The NHS number and NHSBT OTDT Recipient number of all participants will be recorded in the CRF. This will be stored in a password-protected site file.

The following baseline data will be recorded for all eligible participants:

- i. age,
- ii. sex,
- iii. ethnicity.

The following additional baseline data will be recorded for eligible participants who are approached but do not consent to take part in the study:

i. the reason for declining to take part (where given).

The following additional baseline data will be collected for all eligible recipients who consent and receive a transplant:

F-CUSToS Protocol

Version Number 2.0; Dated 30 January 2025

- i. ABO blood group
- ii. Height
- iii. Weight
- iv. BMI
- v. Pathology leading to need for transplant
- vi. 1st, 2nd, 3rd or more heart transplant
- vii. History of Hypertension
- viii. History of Diabetes mellitus
- ix. Renal function (eGFR and serum creatinine)
- x. Liver function (bilirubin)
- xi. Left Ventricular Ejection Fraction prior to transplant
- xii. Current smoker (>5 a day within last 6 months)
- xiii. Use of inotropes at time of transplant
- xiv. Mechanical Circulatory Support immediately prior to transplant
- xv. Previous cardiac surgery
- xvi. Pre-operative mean pulmonary artery pressure, pulmonary capillary wedge pressure, and cardiac output.

7.7 Trial assessments

Assessment of eligibility: Upon trial commencement, the PI at each centre will access the heart transplant waiting list at their centre. Each potential participant will be assessed for eligibility according to the inclusion/exclusion criteria laid out in section 6 of this Protocol. All eligible potential participants will be assigned a unique study identifier and sent an invitation letter. Every interaction should be recorded in the medical notes as per local Trust policies and all trial paperwork should be filed in the Individual Site File (ISF).

When a new patient is added to the centre's heart transplant waiting list the PI of the listing centre should be informed and assess eligibility to participate in the study. If the patient is eligible to participate, they should be assigned a unique study identifier and sent an invitation letter.

Informed consent discussion: Whenever an eligible potential participant has an in-person interaction with their transplant team at their transplant centre, they should be considered for an informed consent discussion. It will be the responsibility of the PI to instigate a system for determining when in-person interactions happen with potential participants. At each in-person interaction, the potential participant should be screened by checking the site file to determine at what stage of the informed consent process they are at. This must include an assessment of whether they have previously declined to consent, in which case they should not be approached again.

Recipient baseline data: The minimum baseline dataset of age, sex and ethnicity should be recorded for all potential transplant recipient participants within two weeks of study initiation. Once an in-person approach to take part in an informed consent discussion has taken place this should be recorded the medical notes. Once the informed consent discussion has taken place the outcome should also be recorded. Possible outcomes include declining to take part, requesting further time to make a decision or consenting to take part. Where the potential participant declines to take part, they should not be approached again, unless they specifically request to take part in another informed consent discussion. Once written evidence of informed consent is obtained from a potential transplant recipient participant,

the individual(s) designated by the PI should input this information into the database. This should be done within 48 hours of written evidence of informed consent being filed in the site file. When a potential participant is called to hospital to receive their transplant, their ongoing consent to take part in the study must be confirmed by a designated individual in that centre. Where consent is withdrawn at this stage this should be recorded by completing the withdrawal of consent form.

Donor baseline data: The donor baseline data outlined in section 7.6.1 will be accessed from the NHSBT transplant registry. This is to avoid duplication of data collection.

Randomisation: The randomisation procedure is outlined in section 7.3 of this Protocol. The outcome of randomisation should be recorded in the CRF, by the delegated individual(s) at the recipient centre.

Organ donation: The organ donation procedure will be carried out in accordance with the UK NORS Protocol. The only change to this Protocol will be the trial treatment, as outlined in section 8 of this Protocol. The outcome of organ donation and the treatment applied should be recorded in the CRF, by the delegated individual(s) at the recipient centre.

Transplant procedure: The transplant implantation procedure will proceed according to the method chosen by the implanting surgeon. There will be no adjustments necessary as a result of taking part in this trial. Operative data will be obtained from the NHSBT Transplant registry and will not need to be recorded in the CRF.

Initial outcome data collection: The delegated individual(s) in the recipient centre should input the CPOi, echocardiogram and PGD data to the database no later than 72 hours after the transplant procedure. This should be conducted in accordance with the blinding instructions laid out in section 7.4 of this Protocol.

CPOi is a calculated variable and will be obtained by uploading the following variables to the database:

- i. Cardiac Output (L/min) measured by Swan-Ganz, using the thermodilution method and taking the average of three measurements, performed as soon as possible, and not later than 1 hour, after admission to ICU.
- ii. Cardiac Output (L/min) measured by Swan-Ganz, using the thermodilution method and taking the average of three measurements, performed 6 hours +/- 2 hours after admission to ICU
- iii. Body surface area calculated using the DuBois and DuBois formula: Body Surface Area= 0.007184 x (Height(m) $^{0.725}$) x (Weight(kg) $^{0.425}$).
- iv. Mean Arterial Pressure (mmHg) on invasive intra-arterial blood-pressure monitoring at the time of Swan-Ganz measurements.
- v. Central Venous Pressure (mmHg) on invasive central venous pressure monitoring at the time of Swan-Ganz measurements.

As this is an exploratory outcome measure, with the intent to assess its utility based on real-world data, this will be assessed based on the above data being recorded on the intensive care electronic health record system. The measurements will be taken and recorded by the healthcare professional(s) looking after the participant. Where the outcome assessor transferring this data from the healthcare record to the trial database cannot find a measurement within the stipulated timeframe, this will be treated as missing data.

PGD will be determined based on the ISHLT consensus statement 2014 (2) and graded accordingly. PGD is defined as occurring within 24 hours, therefore all measurements included below must be taken within the first 24 hours after admission to ICU post-transplant procedure. Its definition requires the following variables to be recorded on the database:

F-CUSToS Protocol

Version Number 2.0; Dated 30 January 2025

- Ejection fraction on echocardiogram; where multiple measurements are taken the lowest estimate of ejection fraction recorded will be inputted to the database.
- ii. Haemodynamic variables taken at the time of a Swan Ganz measurement*:
 - (i) Central Venous Pressure (mmHg)
 - (ii) Pulmonary capillary wedge pressure (mmHg)
 - (iii)Cardiac Output (L/min)
 - (iv) Cardiac Index (L/min/m2)
 - (v) Mean Arterial Pressure (mmHg)
 - (vi)Transpulmonary gradient (mmHg)
 - (vii) Pulmonary artery systolic pressure (mmHg)
- iii. Vasoactive Inotrope Score (VIS), where VIS = dopamine [μ g kg⁻¹ min⁻¹] + dobutamine [μ g kg⁻¹min⁻¹] + 100×adrenaline [μ g kg⁻¹ min⁻¹] + 50×levosimendan [μ g kg⁻¹ min⁻¹] + 10×milrinone [μ g kg⁻¹ min⁻¹] + 10 000×vasopressin [units kg⁻¹ min⁻¹] + 100×noradrenaline dose [μ g kg⁻¹ min⁻¹].
- iv. Presence/absence of an intra-aortic balloon pump (IABP).
- v. Presence/absence of mechanical circulatory support (ECMO/LVAD/RVAD/BiVAD).

*Where multiple Swan Ganz measurements are taken within the first 24 hours after transplant, the set of variables taken at the same time as the highest inotrope score should be uploaded to the CRF. Where there are multiple Swan Ganz measurements with the same inotrope score the set of variables with the lowest cardiac output should be uploaded to the CRF.

The following echocardiographic parameters from trans-oesophageal echo immediately after transplant implantation will be recorded in the initial outcome data collection CRF:

- i. Left Ventricular ejection fraction (% estimated by Simpson's biplane method)
- ii. Left ventricular maximal posterior wall thickness (in mm)
- iii. Maximal septal wall thickness (in mm)
- iv. Left ventricular function (good, moderate, poor or very poor)
- v. Right ventricular function (good, moderate, poor or very poor)
- vi. The presence/absence of any regional wall motion abnormalities as determined by the TOE operator

30-day outcome data collection: The delegated individual(s) in the recipient centre should upload the 30-day mortality, postoperative complication, length of initial ICU stay, and length of initial hospital stay data, on the 31st day after the transplant procedure. This should be conducted in accordance with the blinding instructions laid out in section 7.4 of this Protocol. The variables will be entered into the CRF as follows:

- i. 30-day mortality: alive/dead
- ii. Post-operative complications:
 - (i) Dysrhythmias (any within 30 days):
 - 1. Atrial fibrillation yes/no
 - 2. Ventricular tachycardia yes/no
 - 3. Ventricular fibrillation yes/no
 - 4. Other rhythm abnormality yes/no (specify)
 - (ii) Myocardial Infarction within 30 days (defined according to ESC definitions of myocardial infarction post-cardiac surgery): yes/no

- (iii)Stroke within 30 days (defined by radiological evidence of ischaemia/haemorrhage and clinical symptoms of stroke): yes/no
- (iv)Transplant rejection within 30 days (defined by the clinical team and confirmed on histopathology of biopsy material or post-mortem): yes/no
- (v) Infection within 30 days (from any source requiring antibiotic therapy): yes/no (specify suspected source)
- (vi) Venous thromboembolism within 30 days (defined by radiological evidence and need for treatment): yes/no (specify PE/DVT)
- (vii) 30-day re-admission to any UK hospital: yes/no
- (viii)Hyponatraemia within 24 hours of transplant (Na<125mEq/L on serum sample, not blood gas analysis): yes/no
- (ix) Need for renal replacement therapy (continuous veno-venous haemofiltration or dialysis): yes/no
- iii. Length of initial[†] ICU stay in hours
- iv. Length of initial[†] in-hospital stay in days with admission to ICU taken as the first day and the day of discharge home as the final day, counting inclusive of both.

[†]Initial refers to the first stay only. For example, if a patient is discharged from ICU after 24 hours but re-admitted after 48 hours, the outcome assessor would only record 24 hours as the length of initial ICU stay. Similarly, where a patient is discharged from hospital after 5 days, this would be recorded as 5 days, even if they are subsequently re-admitted and have a longer overall length of stay.

